This preserved effect supports the superiority to placebo because the amount of preserved effect, 6.557% (=77% * M_1), is larger than the placebo-adjusted effect of alendronate 10 mg daily (5.4%; Fosamax® USPI) and of denosumab 60 mg once every 6 months (5.5%; Bolognese 2013) on lumbar spine BMD at 12 months. Furthermore, the placebo-adjusted effect of teriparatide observed in the previous Phase 3 study (Study BA058-05-003) based on an MMRM analysis was 7.841% (95% CI: 7.384%, 8.297%). Thus, the proposed non-inferiority margin leads to 89% (=6.557/7.384) of the effect of teriparatide, another approved anabolic agent.

Non-inferiority of abaloparatide-sMTS to abaloparatide-SC will be concluded if the lower bound of the 2-sided 95% CI for the estimated treatment difference (abaloparatide-sMTS minus abaloparatide-SC) in the percent change from baseline in lumbar spine BMD at 12 months is above -2.0%, using an MMRM analysis.

A sample size of 426 subjects will provide at least 90% power to conclude the non-inferiority of abaloparatide-sMTS 300 μ g to abaloparatide-SC 80 μ g, assuming a true mean difference of zero percent and a standard deviation of 6.35%. To ensure an analysis size of 426 subjects, an overall sample size of 474 subjects (237 subjects per group) will be randomized, anticipating that approximately 10% of treated subjects may not have both a baseline lumbar spine BMD measurement and at least 1 post-baseline lumbar spine BMD measurement.

Statistical Methods:

Analysis Populations:

The modified Intention-to-Treat (mITT) Population, defined as all randomized subjects who received at least 1 dose of study drug and had a baseline lumbar spine BMD measurement and at least 1 post-baseline lumbar spine BMD measurement, will be the primary population for the analyses of all efficacy endpoints. Supportive analyses of efficacy will be conducted using the Intention-to-Treat (ITT) Population, defined as all subjects randomized into the study, and the Per-Protocol (PP) Population, defined as all subjects in the mITT Population who did not have any critical protocol deviations (as defined in the Statistical Analysis Plan). The primary population for safety analyses will be the Safety Population, defined as all randomized subjects who received at least 1 dose of study drug.

Baseline Comparison:

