4.7. Temporary Suspension of Treatment

The Investigator has the right to suspend treatment with study drug for up to 14 continuous days. Subjects can miss up to 28 cumulative days of dosing without withdrawal of the subject from the study. Reasons for temporary suspension of treatment may include a medical reason unrelated to an AE (eg, a planned procedure) or important social or administrative events. The reason for the suspension of treatment is to be documented and source verified during monitoring visits.

When treatment is restarted, the subject should resume treatment with the next scheduled dose and continue until the scheduled EOT.

Subjects who develop hypercalcemia or hypercalciuria during the study are to have treatment with calcium and vitamin D temporarily suspended as described below. The Investigator should contact the sponsor for any planned suspension of treatment or if suspension of treatment is contemplated.

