### **4.3. Exposure to Study Drug**

#### **4.3.1. Extent of Exposure and Treatment Compliance**

Subjects were trained by study personnel on how to self-administer study drug with the abaloparatide-SC injection pen or the abaloparatide-sMTS patch. On the days of study site visits, study drug must be administered at the study site to accommodate pre-administration and post-administration procedures.

The overall duration of study drug exposure will be calculated using the data recorded on the eCRF as follows:

- Overall duration of study drug exposure (days) = (date of last dose – date of first dose) + 1.

If the date of last dose is missing, then the earlier of the following 2 dates will be used as the last dose date for analysis and summary purposes: the final visit/early termination visit date or the last drug dispense date + 30 days.

For the abaloparatide-SC group, the total number of doses delivered and study drug administration compliance will be calculated in two ways as follows:

- **Based on missed doses in subject diary:**
  - Number of doses delivered = Overall duration of study drug exposure – Total number of missed doses per subject diary
  - Percent compliance (%) to study drug administration =  $(\text{Number of doses delivered} / \text{Overall duration of study drug exposure}) \times 100\%$
- **Based on measurement of drug remaining in pen:**
  - Number of doses delivered =  $[(45.5 \text{ mm} \times \text{Number of used pens}) - \text{Sum of measurements of drug remaining in all used pens}] / 1.08 \text{ mm}$ . Here the 45.5mm is the initial measurement of unused study drug in an unused injection pen and 1.08mm is the distance the plunger travels for each 80 ug dose from the pen.

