    - Note: If the measurement of drug remaining in any used pen is missing, then 100% compliance will be assumed for the intended treatment period for which the pen with missing measurement of drug remaining was dispensed. For each pen dispensed prior to Month 11 visit, the intended treatment period is a 30-day period starting from the day when first dose was taken from the pen. For the pen dispensed at Month 11 visit, the intended treatment period is a period less than or equal to 30 days starting from the day when first dose was taken from the pen to the EOT day. The number of doses taken from the pen with missing measurement of drug remaining is a value less than or equal to 30, which will be based on the number of doses taken from the pen(s) with non-missing measurement of drug remaining and the duration of the treatment period. The number of doses delivered would be the minimum of the following:
      - Total doses taken from pens with non-missing measurements of drug remaining (calculated as:  $[45.5 \text{ mm} \times \text{Number of pens with non-missing measurements of drug remaining} - \text{Sum of measurements of drug remaining from all pens with non-missing measurements of drug remaining}] / 1.08 \text{ mm}$ ) +  $30 \times \text{number of pens with missing measurement of drug remaining}$
      - Overall duration of study drug exposure (last dose date - first dose date + 1)
    - Percent compliance (%) to study drug administration =  $(\text{Number of doses delivered} / \text{Overall duration of study drug exposure}) \times 100\%$

For the abaloparatide-sMTS group, the total number of doses delivered and study drug compliance will be calculated in two ways as follows:

- **Based on missed doses in subject diary:**
  - Number of doses delivered = Overall duration of study drug exposure - Total number of missed doses per subject diary
  - Percent compliance (%) to study drug administration =  $(\text{Number of doses delivered} / \text{Overall duration of study drug exposure}) \times 100\%$
- **Based on number of patches returned:**
  - Number of doses delivered =  $20 \times \text{Number of kits dispensed} - \text{Sum of patches returned in all dispensed kits}$ . The number of patches dispensed per kit is 20.

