### **3. Other date imputations**

Any event with a partial date that requires imputation but has no specific imputation rule will be imputed as follows:

- If the day is missing, then impute the day as '01'
- If the month is missing, then impute the month as 'JUL'
- If the imputation of a start date causes the start date to be post the non-missing end date, then the start date will be imputed as the end date.
- If the imputation of a start date causes the start date to be prior to the start of treatment (but the event should happen post-baseline), then the start date will be imputed as "treatment start date + 1."
- Any date cannot be imputed past the date of death. When this happens, the date will be imputed as the date of death.

**Appendix B. Algorithm to Identify Critical Protocol Deviations that Exclude Subjects from the Per-Protocol (PP) Population**

The below algorithm outlines the criteria for identifying critical protocol deviations. Subjects with at least one of these critical protocol deviations will be excluded from the PP population.

- A. Deviations of subject eligibility (Inclusion/Exclusion criteria) that will result in exclusion from PP population (refer to the protocol for the complete text of each inclusion/exclusion criterion below):
  - 1. Inclusion Criterion #2: Less than 5 years postmenopausal.
  - 2. Inclusion Criterion #3: A BMD T-score outside the required range or fracture criteria not met.
  - 3. Exclusion Criterion #1: History of more than 4 spine fractures, mild or moderate, or any severe fractures.
  - 4. Exclusion Criterion #2: Presence of abnormalities of the lumbar spine that would prohibit assessment of spinal bone mineral density (BMD).
  - 5. Exclusion Criterion #3: Unevaluable hip BMD or subjects who have undergone bilateral hip replacement.
  - 6. Exclusion Criteria #4, #5, #6: Diseases and treatments affecting bone strength.
  - 7. Inclusion Criterion #5: Laboratory tests affecting the bone strength.
  - 8. Exclusion Criteria #16, #17, #18, #19, #20, #21, #22, #23, #24 and #26: Prior treatment with bone-acting agents within the specified time periods.
- B. Deviations of study drug administration that will result in exclusion from PP population:
  - 1. Duration of study drug exposure is less than 3 months (90 days)
  - 2. Compliance to study drug administration < 80%
- C. Deviations of efficacy measurements that will result in exclusion from PP population:
  - 1. Lumbar spine BMD is missing at baseline

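### Early stopping never counts as non-compliance in the per-protocol rules, and no rule removes bone density scans taken after drug has stopped, so the per-protocol analysis is a weaker check against dilution than it should be.

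*Protocol*

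**What the plan says.** The synopsis (Analysis Populations) has the PP population "defined as all subjects in the mITT Population who did not have any critical protocol deviations". Protocol 8.3.1 likewise leaves the exclusion criteria to the SAP and makes PP supportive to mITT.

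SAP Appendix B, part B, gives two dosing criteria for exclusion: "Duration of study drug exposure is less than 3 months (90 days") and "Compliance to study drug administration < 80"%.

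SAP 4.3.1 defines the quantities:
- Exposure: "Overall duration of study drug exposure (days) = (date of last dose – date of first dose) + 1".
- Doses, diary method: "Number of doses delivered = Overall duration of study drug exposure – Total number of missed doses per subject diary".
- Compliance: doses delivered divided by that same exposure duration. The denominator is the same in both arms and for both counting methods (diary; pen measurement or patch count).
- A woman is excluded only if both compliance calculations are below 80%. Appendix B item B.2 does not repeat that condition.

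Appendix B item D.1 is a catch-all for deviations with potential major impact on the efficacy endpoint. It names prohibited medication but not early discontinuation. SAP 2.2 describes critical deviations as those with the potential to affect efficacy.

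SAP Table 3 assigns BMD scans to Month 3 (Days 2–120), Month 6 (Days 121–300) and Month 12 (Day 301 onward). Protocol 4.3.1 speaks of terminating study drug and/or discontinuing the subject, and SAP 4.1 tabulates drug discontinuation separately from study discontinuation.

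**The concern.** In a non-inferiority trial, a PP analysis is meant to show that similarity between arms was not produced by diluted treatment. Under these rules, stopping early shortens the numerator and the denominator of compliance together, so it can never lower compliance. Once 90 days of exposure are reached, nothing in the dosing criteria limits how much of the 12-month course is lost after the last dose.

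A woman can therefore be counted as per protocol after a quarter of the planned course. If she stays in follow-up and is scanned at about Day 360, a value measured some nine months off drug enters the PP analysis as her Month 12 result. If such scans are common and similarly frequent in both arms, a true deficit of the patch could look smaller in PP than it would on drug, and PP would not reveal what it is there to reveal.

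**Working it through.** **Inputs.** Once-daily dosing for 12 months of 30 days (synopsis), so 360 planned doses. PP cut-offs of 90 days and 80% (SAP Appendix B). Compliance = doses / (last dose − first dose + 1) (SAP 4.3.1). Margin 2.0, SD 6.35, 426 analysed (Protocol 8.5).

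**The plan's own figure.** The documents give no figure for the PP rule. The sample size reproduces: 213 per arm, SD 6.35, margin 2.0 and true difference 0 give 90.03% power (noncentral t), and 426 / 0.90 = 473.3, rounded up to 474.

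**The PP rule applied.** Each woman is assumed to have no other critical deviation.

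| Doses / own duration | Compliance | PP status | Share of 360 |
|---|---|---|---|
| 91 / 91 | 100% | kept | 25.3% |
| 90 / 90 | 100% | kept | 25.0% |
| 72 / 90 | 80.0% | kept | 20.0% |
| 288 / 360 | 80.0% | kept | 80.0% |
| 270 / 360 | 75.0% | excluded if both calculations agree | 75.0% |

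**How an off-drug scan enters.** If the woman who stops at Day 91 stays in the study and is scanned at Day 360, the scan is 360 − 91 = 269 days after her last dose. Table 3 labels it Month 12, and no PP criterion removes it.

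**How it often will not.** Protocol 4.3.2 asks women withdrawn before 12 months to complete the Month 12/EOT procedures as soon as possible. A scan soon after Day 91 falls in the Month 3 window, and one soon after Day 200 falls in Month 6. Month 12 is then missing and handled under the MMRM's missing-at-random assumption. If the scan follows the last dose within 14 days, a scan at Day 301 or later implies a last dose at Day 287 or later, about 80% of the course (287/360 = 79.7%).

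**Direction.** Let p be the share of PP women in an arm with an off-drug Month 12 scan, and L their mean loss of BMD gain. Then

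observed difference = true difference + p(SC)·L(SC) − p(sMTS)·L(sMTS).

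With equal p, and a larger loss in the arm that gained more, the difference moves toward zero. If more patch users stop, it can move the other way.

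**Illustrative size (assumptions, not document figures).** Take a true deficit of 2.0, p equal in both arms at 5%, 10% or 15%, and a fraction g of the deficit lost in these women. The shift is 2.0 × p × g. SE = 6.35 × √(2/213) = 0.615. The chance that PP alone shows non-inferiority is P(Z > 1.96 − shift/0.615).

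| p | g = 0.6: shift, rate | g = 1 (whole deficit lost): shift, rate |
|---|---|---|
| 0 | 0, 2.5% | 0, 2.5% |
| 5% | 0.06, 3.1% | 0.10, 3.6% |
| 10% | 0.12, 3.9% | 0.20, 5.1% |
| 15% | 0.18, 4.8% | 0.30, 7.1% |

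The SE uses the mITT target. PP is a subset of mITT, so its SE would be somewhat larger and these rates somewhat lower for the same shift.

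**The case against.** The strongest reply is that the planned course produces few such scans. Protocol 4.3.2 brings the final scan forward, the EOS visit has no DXA, and several passages link stopping or missing drug to possible withdrawal from the study (Protocol 4.7, 4.7.1, 5.7). This stands, and it is why the effect is probably small. It does not close the gap: Protocol 4.3.2 is written for women withdrawn or discontinued from the study, while Protocol 4.3.1 and SAP 4.1 also allow for women who stop drug and remain.

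Item D.1 could be read to remove an early stopper. But it does not name early discontinuation, and the resulting exclusion list is reviewed after database lock (SAP 2.2), so the outcome would rest on judgement.

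Three stronger readings are tempting and are not supported.
- A reader might infer that the PP set is upside down because a woman with 270 doses over 360 days is excluded. Excluding her is proper: she missed 90 days, and Protocol 4.7 says "Subjects can miss up to 28 cumulative days of dosing without withdrawal of the subject from the study". Her exclusion also needs both calculations below 80%, and missing pen measurements or kit returns are credited as full compliance. Nor is that 28-day allowance like for like with days after the last dose, since it concerns doses missed during treatment.
- A reader might infer that the error always favours non-inferiority. That needs similar stopping in both arms, which cannot be presumed in an open-label comparison of a patch with an injection.
- A reader might infer that the trial's false-positive rate is inflated. PP is supportive; the conclusion rests on the mITT MMRM.

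**Conclusion.** The point holds as a weakness of a supportive analysis. Early stopping is invisible to PP compliance: a woman who stops at Day 91 with no missed doses is retained with about 25% of the planned doses, and nothing in the PP rules excludes a scan because drug had already stopped. Off-drug Month 12 scans can therefore enter the PP MMRM and dilute the comparison that PP is meant to protect.

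The size cannot be taken from the documents. It depends on how many women stop drug after Day 90 yet have a scan at Day 301 or later, and on how much of the between-arm difference is lost in them. It is near zero if there are no such scans. Under the equal-stopping assumptions above, at a true deficit of 2.0, PP would show non-inferiority 3.1% to 7.1% of the time instead of 2.5%. The mITT primary analysis and the 426/474 sample size are untouched.

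**What to change.** In the PP MMRM only, exclude any BMD scan taken more than a pre-specified interval after the last dose. Fourteen days is one example, borrowed from the longest continuous suspension in Protocol 4.7; it is an analysis convention and needs its own short justification. State the rule in SAP Appendix B, SAP 4.4.1.2 and the Per-Protocol Memo before database lock. In the same edit, align Appendix B item B.2 with the condition in SAP 4.3.1 that both calculations fall below 80%.

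This keeps on-drug Month 3 and Month 6 data from early stoppers and drops only off-drug values. The cost is SAP wording, a few lines of programming and somewhat fewer Month 12 scans in PP.

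Compliance against the planned 360 days (an 80% bar of 288 doses) may be shown as an additional sensitivity set. It should not be the required PP definition: it would make PP close to a completers' set, selected on discontinuation after randomization, and would discard valid on-drug scans. Leave the mITT primary analysis as it is.

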1. INTRODUCTION

1.1. Background

Human parathyroid hormone (PTH) is a naturally occurring 84 amino acid hormone and is primarily a regulator of calcium homeostasis (Mannstadt 1999). PTH acts directly on bone to increase calcium resorption, on the gastrointestinal system to increase calcium absorption, and on the kidney to increase calcium reabsorption and 1,25-dihydroxyvitamin D production. In turn, PTH levels are tightly regulated by calcium and vitamin D levels. When given intermittently at low doses, PTH has a well-documented anabolic effect on bone and can increase bone mineral density (BMD) in a number of intact animal models and in osteoporotic patients (Dempster 1993).

Abaloparatide (marketed as TYMLOS® in the United States [US]) was approved for use on April 28, 2017 in the US for the treatment of postmenopausal women with osteoporosis at high risk for fracture. Abaloparatide is a novel, synthetic, 34 amino acid peptide designed to be a potent and selective activator of the PTH/PTH-related protein (PTHrP) type 1 receptor (PTHR1) signaling pathway with 41% homology to PTH[1–34] and 76% homology to human PTHrP[1–34]. Abaloparatide is differentiated from PTH and PTHrP ligands based on its high affinity and >1,000-fold greater selectivity for the G protein-coupled (RG) vs the non-G protein-coupled (R³) conformation of PTHR1 (Hattersley 2016). Differential PTHR1-RG binding with abaloparatide results in potent and transient intracellular cyclic adenosine monophosphate signaling. In nonclinical studies, the transient PTHR1 activation with abaloparatide strongly favors bone anabolism with a limited effect on bone resorption (Makino 2015). Thus, abaloparatide was developed with the expectation that it would be effective at increasing bone mineral density (BMD) and reducing fracture in individuals with osteoporosis, but with a limited effect on bone resorption and a reduced risk of hypercalcemia.

Abaloparatide is supplied in a single-patient-use prefilled pen that delivers 80 µg of abaloparatide as a subcutaneous (SC) injection into the periumbilical region of the abdomen. Abaloparatide administered as a SC injection is referred to throughout this document as abaloparatide-SC. The sponsor, in collaboration with 3M, has developed a short wear time transdermal method of administration for abaloparatide to provide an alternative route of administration that may be preferred by some patients, thus, reducing a barrier for anabolic therapy. This is referred to as the abaloparatide-solid microstructured transdermal system (abaloparatide-sMTS).

Abaloparatide-sMTS is a drug device combination product consisting of the drug (abaloparatide) and excipient (zinc chloride [ZnCl₂]) coated onto the sMTS array and contained within the following packaging system:

- The primary packaging components with a delivery function includes:
 - o An array patch for adhering the drug formulation-coated sMTS array to the skin
 - A tray that holds and protects the coated array patch and inserts it into an applicator
- The primary packaging components with a protective function includes:

- o A pod that holds the insert
- o A lid heat sealed to the edges of the pod
- The secondary packaging includes:
 - A desiccant
 - o A foil patch, heat sealed, that contains the sealed pod and desiccant

The applicator is a spring powered device that, when pressed against the skin of the thigh, inserts the drug formulation-coated sMTS array tips into the dermis at a predetermined force. In contrast to traditional transdermal delivery systems, the sMTS array penetrates the stratum corneum to deliver the drug formulation following a short wear time (ie, 5 minutes).

1.1.1. Disease and Study Drug Background

Osteoporosis is a systemic skeletal disease characterized by low bone mass and microarchitectural deterioration of bone tissue that leads to enhanced fragility and increased risk of fractures (Rizzoli 2001). This disease is characterized by low BMD and fractures. The fractures associated with the greatest morbidity and mortality, as well as economic burden to society, together make up the clinically significant and medically relevant group termed major osteoporotic fractures. In the US, there are an estimated 2 million osteoporotic fractures annually (Litwic 2014). The number of osteoporotic fractures is projected to increase in both men and women by more than 3-fold over the next 50 years as a result of the aging population (World Health Organization [WHO] 2007).

Spinal fractures have also been associated with poor outcomes and high mortality rates (Suzuki 2008). It has been reported that once a patient has sustained a vertebral fracture, the risk of a subsequent vertebral fracture increases by >300% and the risk of a subsequent hip fracture increases by 200% (Black 1999). Additional studies have shown that almost half of the patients with a prior vertebral fracture will experience additional vertebral fractures within 3 years, many within the first year (Robinson 2002; Lindsay 2001). Those patients who sustained a vertebral body fragility fracture showed a prolonged course that can lead to significant disability even 1 year later (Suzuki 2008). Patients with a diagnosis of osteoporosis who have had any fracture have an 86% increase in their risk for another fracture (Kanis 2003). With the severity of these implications, prevention of a secondary fracture has become a primary focus from a patient care and societal standpoint.

Major osteoporotic fractures (those of the wrist, shoulder, hip and clinical spine) account for 94% of the fracture risk for women with low or minimal trauma (Ensrud 2016). Major osteoporotic fractures contribute to accumulated frailty such that the Frailty Index is significantly larger in those elderly women who have experienced a major osteoporotic fracture. As a result, these women have worsening frailty and greater morbidity after a major osteoporotic fracture (Li 2014). The Frailty Index was associated with a predicted increase in the risk of falls, fractures, death and overnight hospitalizations (Li 2014). Consequently, prevention of clinically significant and medically relevant major osteoporotic fractures will reduce health care costs and benefit postmenopausal women due to reduced frailty, reduced risk of falls, fractures, hospitalizations and death.

Bone remodeling occurs through the action of osteoclasts, which are involved in the resorption of bone followed by the formation of new bone by osteoblasts. In addition to continued use of calcium and vitamin D, the current therapeutic approach to the treatment of osteoporosis through inhibition of bone resorption includes agents such as bisphosphonates (Rosen 2005) or the monoclonal antibody denosumab, that inhibits the action of osteoclasts by binding to receptor activator of nuclear factor kappa-B ligand. An alternative approach has been to tip the balance between osteoblastic bone formation and osteoclastic resorption through the use of parathyroid hormone receptor modulation using teriparatide (rhPTH[1–34]).

Until recently, teriparatide has been the only approved osteoporosis treatment in which the major mode of action is stimulation of bone formation (anabolic) rather than suppression of bone resorption. The efficacy of teriparatide has important limitations related to its delayed and modest effects on increasing BMD at the total hip and femoral neck and decreasing BMD at the distal 1/3 radius. The increase in cortical porosity that can occur may result in maladaptive effects on cortical bone microarchitecture (Bilezikian 2007). Abaloparatide has been evaluated in a number of nonclinical and clinical studies for its potential as a novel treatment for osteoporosis. Based on the biology of the PTH₁ receptor signaling pathway, abaloparatide is designed to have less resorptive and hypercalcemic effects than PTH, resulting in a greater net anabolic effect.

